2.2.4 Combination of Regorafenib and Anti-PD-1 Antibody

The rationale for combining immunotherapy with anti-angiogenic treatments has been outlined by Khan and Kerbel (Khan and Kerbel 2018) and is supported by both pre-clinical and clinical results in various indications including HCC (Ikeda et al. 2018, Kato et al. 2019).

Pre-clinically, the combination of regorafenib with anti-PD-1 demonstrated beneficial anti-tumor activity versus single agents in mouse models of colorectal cancer (CRC) (Hoff et al. 2017), melanoma (Wu et al. 2019), and HCC (data on file).

Mechanistically, this effect may be mediated by

- 1. a reduction/reprogramming of tumor associated macrophages by the inhibition of the CSF1R by regorafenib (Hoff et al. 2017).
- 2. suppression of interferon gamma induced PD-L1 and indolamine-2,3-dioxygenase (IDO1) expression, with minor effects on major histocompatibility complex 1 (MHC1) expression due to inhibition of RET and RAF (Wu et al. 2019).
- 3. increased infiltration of cytotoxic T cells in HCC tumors, mediated by elevated expression of CXCL10 (the ligand for CXCR3), which occurs on T cells (data on file).

Furthermore, VEGF signaling is known to suppress immune activity either directly on immune cells or indirectly by affecting the tumor vasculature (Khan and Kerbel 2018). Regorafenib as a potent VEGFR kinase inhibitor may thereby attenuate the immunosuppressive effects of VEGF. Inhibition of VEGFR and its signaling pathway may normalize tumor blood vessels and improve cytotoxic T cell infiltration (Zopf et al. 2016). Immune checkpoint inhibitors appear to affect the tumor vasculature as well, which may synergize with the inhibition of VEGF signaling by regorafenib (Tian et al. 2017).

Page 33 of 141

Additional clinical evidence of the potential synergistic effects of combining immune checkpoint inhibitors with VEGF inhibitors is also derived from REGONIVO, an open-label, dose-finding, and dose-expansion Phase 1b study of regorafenib and nivolumab in patients with advanced microsatellite-stable CRC and gastric cancer (Fukuoka et al. 2019). The combination was tolerable and an encouraging 38% ORR was observed across tumor types.

A multicenter, non-randomized, open-label dose escalation Phase 1b study of regorafenib in combination with pembrolizumab in patients with advanced HCC with no prior systemic therapy (study 19497) is currently being conducted to determine the safety and tolerability of regorafenib in combination with pembrolizumab. Preliminary data from this trial (NOV 2020) did not result in any new safety signals considering the safety profile of either drug alone, and also showed promising anti-tumor activity (ORR 29%, DCR 94%, for patients treated at the 120mg MTD).

2.3 Benefit/Risk Assessment

2.3.1 Risk Assessment

Both regorafenib and pembrolizumab have manageable and well-understood safety profiles, and no new safety signals have been seen with the combination to date in HCC.

Pembrolizumab is generally well-tolerated but can induce immune-related adverse events (irAEs). Study participants will be closely monitored for development of irAEs and will receive treatment such as administration of corticosteroids, anti-inflammatory therapies, and other appropriate supportive care measures. Overlapping side effects such as liver toxicity, diarrhea, and skin reactions are possible. More detailed information about the known and expected benefits and risks, and expected AEs of regorafenib and pembrolizumab can be found in the most recent IB of each drug.

Additional considerations on safety monitoring: every effort will be made to minimize AEs of this drug combination during the study, through participant selection (e.g., only Child-Pugh A patients will be enrolled) and extensive safety monitoring. Special importance will be given to liver toxicity, as fatal cases of liver failure following toxic hepatitis have been reported in adult patients on regorafenib, and as there is a potential overlapping toxicity with pembrolizumab. Liver function tests will be closely monitored in all participants (weekly for the first 8 weeks and then monthly with mandatory assessments before each regorafenib treatment cycle).

No drug-drug interaction between regorafenib and pembrolizumab is expected because pembrolizumab is a therapeutic monoclonal antibody that is not metabolized and is also not a cytokine modulator. This is supported by preliminary pharmacokinetics (PK) data from the ongoing Phase 1b study 19497 indicating that regorafenib exposure, when administered in combination with pembrolizumab, is similar to regorafenib monotherapy. Since pembrolizumab is cleared by nonspecific proteases, similar to endogenous proteins, no effect of regorafenib on pembrolizumab PK is expected.

2.3.2 Benefit Assessment

Regorafenib is a potent MKI with an extensive kinase-inhibition profile, exhibiting robust efficacy data in pre-treated HCC patients. The RESORCE study showed similar clinical benefit for regorafenib for the second line setting as observed with sorafenib in the first line. This observed level of clinical benefit in a pre-treated population suggests that regorafenib

Page 34 of 141

has the potential to offer benefit in a patient population previously treated with other 1L systemic therapy, justifying studying it in the 2L setting.

Recently published data support the combination of an MKI with an anti-PD-L1 as an option for treatment-refractory cancer such as metastatic RCC after progression with a PD-1/PD-L1 immune checkpoint inhibitor. In the Phase 2 trial of lenvatinib in combination with pembrolizumab for disease progression after PD-1/PD-L1 immune checkpoint inhibitor in metastatic RCC, 65% of patients had prior PD-1/VEGF combination therapy and 37% had prior ipilimumab/nivolumab during a median prior duration of immunotherapy of 7 months. The objective response of the study treatment combination was of 51%, with a median PFS of 11.7 months and median DOR of 9.9 months (Lee et al. 2020).

Immune checkpoint inhibitors have shown promising clinical activity and durable responses in patients with HCC. Based on complementary modes of action between MKIs and PD-1 inhibitors and their potentially synergistic effects on the cancer-immunity pathway, the combination of regorafenib and pembrolizumab might provide a greater clinical benefit in HCC patients.

Preliminary data from the Phase 1b study 19497 of regorafenib in combination with pembrolizumab in patients with advanced HCC with no prior systemic therapy have demonstrated a potential efficacy signal in 1L and a tolerable safety profile. As of NOV 2020, 9 out of the 31 participants who started 120 mg regorafenib QD (3 weeks on / 1 week off) and pembrolizumab 200mg Q3W and were evaluable for efficacy achieved PR per RECIST 1.1, with a DCR of 94%. Of the 21 patients who started 80 mg regorafenib QD (3 weeks on / 1 week off) and pembrolizumab 200mg Q3W and were evaluable for efficacy, 3 achieved PR per RECIST 1.1, with a DCR of 86%. Efficacy data for the 80 mg cohort were immature as of the cut-off date for this analysis.

2.3.3 Overall Benefit / Risk Assessment

In preclinical and clinical studies, regorafenib has demonstrated potent anti-tumor activity as a single agent in a broad spectrum of tumor models including hepatocellular tumor models, which is likely mediated by its anti-angiogenic and anti- proliferative effects. A positive benefit to risk profile is expected and combining regorafenib with an anti-PD-1 such as pembrolizumab is a potential and promising second line therapeutic option in advanced liver cancer.

Based on the data available to date, the conduct of the clinical trial is regarded as justified.

3. Objectives and Endpoints

The purpose of this study is to evaluate the efficacy and safety of regorafenib in combination with pembrolizumab for the treatment of advanced HCC in adult participants who have been previously treated with a PD-1/PD-L1 immune checkpoint inhibitor. The objectives and endpoints for the study are summarized in Table 3–1.

Table 3-1: Objectives and Endpoints

Objectives	Endpoints
Primary	
To demonstrate the objective anti-tumor activity of regorafenib in combination with pembrolizumab as 2L treatment for advanced HCC	ORR per RECIST 1.1 ^a by central assessment

Table 3-1: Objectives and Endpoints

Objectives	Endpoints
Secondary	Επαροπτισ
To evaluate other measures of anti-tumor activity of regorafenib in combination with pembrolizumab as 2L treatment for advanced HCC	 DOR per RECIST 1.1 by central assessment ORR per RECIST 1.1 by investigator assessment DOR per RECIST 1.1 by investigator assessment
To evaluate safety and tolerability of regorafenib in combination with pembrolizumab	 Number of participants with AEs Number of participants with SAEs Number of participants with safety-relevant changes in clinical parameters Number of participants with dose modification (dose interruption, dose reduction, dose discontinuation)
Tertiary/Exploratory	
To establish further exploratory indicators of efficacy of regorafenib in combination with pembrolizumab	 DCR per RECIST 1.1 by central assessment and investigator assessment PFS as per RECIST 1.1 by central assessment and investigator assessment Overall survival (OS) ORR per HCC mRECIST and iRECIST by investigator assessment DOR per HCC mRECIST and iRECIST by investigator assessment
 To evaluate the PK of regorafenib when concomitantly administered with pembrolizumab To evaluate PK and immunogenicity of pembrolizumab when concomitantly administered with regorafenib 	Exposure of regorafenib and pembrolizumab, and incidence of anti- drug antibody (ADA) for pembrolizumab
 To identify biomarkers in baseline tumor materials and/or blood that may associate with response To explore pharmacodynamic effects of regorafenib and pembrolizumab combination To evaluate the PK/pharmacodynamic relationship for correlative biomarkers in blood such as peripheral lymphocytes, circulating proteins or nucleic acids (DNA or RNA), and/or tissues as well as measures of safety and/or efficacy To further investigate the study intervention and similar drugs (i.e., mode-of-action-related effects and/or safety) and to further investigate pathomechanisms deemed relevant to cancer and associated health problems 21 = second line: ADA = anti-drug antibodies: AF = advertised 	 Correlation of biomarkers before treatment with other study endpoints Change from baseline in levels of biomarkers in blood or tumor Retrospective exploratory analysis of the relationship between regorafenib exposure and biomarker, safety and/or efficacy measures Various biomarkers (e.g., diagnostic, safety, pharmacodynamic, monitoring, or potentially predictive biomarkers)

²L = second line; ADA = anti-drug antibodies; AE = adverse event; DCR = disease control rate; DNA = deoxyribonucleic acid; DOR = duration of response; HCC = hepatocellular carcinoma; ORR = objective response rate; OS = overall survival; PFS = progression-free survival; PK = pharmacokinetics; RECIST = Response Evaluation Criteria in Solid Tumors; RNA = ribonucleic acid; SAE = serious adverse event

a. See Appendix 5 (Section 10.5) for tumor response criteria RECIST 1.1, HCC mRECIST, and iRECIST

Additional 67 patients

4. Study Design

4.1 Overall Design

Figure 4-1: Study Design

This is an open-label, Phase 2 trial to evaluate efficacy and safety of regorafenib in combination with pembrolizumab in patients with advanced HCC post PD-1/PD-L1 immune checkpoint inhibitors, in monotherapy or combination regimens.

This study will investigate if the combination of regorafenib with PD-1 inhibitor pembrolizumab can improve the clinical outcome for patients with advanced HCC in the second line setting and follows a two phase design, consisting of an initial pilot phase and an expansion phase (see Figure 4–1):

- a) Pilot phase: Approximately 52 participants will be enrolled to receive regorafenib in combination with pembrolizumab
 - o **Cohort 1:** 26 participants after one systemic line of therapy consisting of atezolizumab plus bevacizumab treatment combination only
 - Cohort 2: 26 participants after one systemic line of therapy consisting of any IO containing first line treatment (excluding atezolizumab with or without bevacizumab) in monotherapy or combination regimens
- b) Expansion phase: If the target ORR is achieved in the pilot phase (i.e. at least 8 responders out of 26 treated in cohort 1 or at least 8 responders in each cohort), the study can enroll approximately 67 new additional participants. These additional participants can be from cohort 1 (i.e. patients progressing on atezolizumab plus bevacizumab combination) or the combined population from cohort 1 plus cohort 2 (i.e., patients progressing on any immune checkpoint inhibitor), depending on which cohorts meet the response rate criteria for expansion (see Section 9.2).

Results from the pilot phase will inform the selection of the appropriate population for further study in the expansion phase.

Patients with Regorafenib 90 mg Pilot phase advanced HCC starting dose (120 mg approximately 52 patients dose escalation) progressed on 1L • Cohort 1: 26 patients after anti-PD-1/PD-L1 3W on/1W off ₽ atezolizumab plus bevacizumab therapy treatment combination • ECOG 0/1 • Cohort 2: 26 patients after any IO Pembrolizumab • Child-Pugh A containing first line treatment 400 mg IV Q6W If target ORR achieved in Cohort 1, or in both Cohorts **Expansion phase**

ECOG = Eastern Cooperative Oncology Group performance status; HCC = hepatocellular carcinoma; IV = intravenous; IO = immune oncology; ORR = objective response rate; PD-1 = Programmed cell death 1; PD-L1 = Programmed death-ligand 1; Q6W = every 6 weeks; W = week

Page 37 of 141

4.1.1 Study Periods

4.1.1.1 Screening Period

The start of the screening phase is defined by signing of the ICF. Participants will be screened for eligibility up to 28 days immediately prior to W1D1.

During this time, the inclusion and exclusion criteria will be assessed and all screening procedures will be performed. Results of all screening/baseline evaluations must be reviewed by the investigator or his/her designee prior to assignment to treatment of each participant into the study to ensure that all inclusion and exclusion criteria have been satisfied. See the schedule of activities (SoA) in Section 1.3.1 for the procedures during the screening period.

4.1.1.2 Intervention Period

The start of the intervention period is defined by the first administration of the combination study intervention.

Participants will be treated with 400 mg pembrolizumab IV Q6W.

Regorafenib will be given orally (p.o.) at a starting dose of 90 mg QD for 3 weeks of every 4 weeks (i.e., 3 weeks on, 1 week off). If the starting dose of 90 mg daily is well tolerated (absence of any grade rash/hand-foot skin reaction [HFSR] or other Grade 2 or higher clinically significant toxicity), the dose can be escalated to 120 mg daily any time after the first cycle of regorafenib, starting with W5D1. Dose modification guidelines for dose reduction in case of toxicity are detailed in Section 6.6.

To support participants in establishing the drug intake rhythm (i.e. 6-week cycle for pembrolizumab, 4-week cycle for regorafenib), the site personnel are asked to call participants regularly for at least the first 3 regorafenib treatment cycles to remind them of omitting regorafenib during the 4th week of a cycle.

Participants will continue to receive study intervention until disease progression as defined by RECIST 1.1, unacceptable toxicity, consent withdrawal, withdrawal from the study at the discretion of the investigator or his/her designated associate(s), or until any other withdrawal criteria are met. Treatment beyond radiological progression is possible if the participant is still benefiting from treatment (see Section 6).

Participants who complete 18 infusions of pembrolizumab need to discontinue treatment with pembrolizumab. Regorafenib treatment can be continued beyond 2 years until withdrawal criteria are met. Treatment with individual drugs (regorafenib or pembrolizumab) may continue on schedule even if the other drug is interrupted or permanently discontinued due to toxicity.

During the study, participants will undergo evaluations for safety, efficacy, PK, and tissue and blood/plasma for biomarker will be collected. See the SoA in Section 1.3 for the assessments during the intervention period.

4.1.1.3 Active Follow-up

A mandatory safety follow-up visit will take place 30 days (window of +7 days) after the last administration of the last study intervention (regorafenib and/or pembrolizumab).

If applicable, an additional safety follow-up must occur 90 days (window of +7 days) after the last pembrolizumab administration. Longer safety follow-up for pembrolizumab is required due to the long half-life of the antibody. Note: If pembrolizumab is permanently discontinued first and the day 30 or the day 90 safety follow-up visit after the last infusion of

Page 38 of 141

pembrolizumab falls into the regorafenib treatment period or regorafenib day 30 safety follow-up visit, no separate pembrolizumab day 30 or day 90 safety follow-up visit is necessary as the information gathering and examinations will occur with regorafenib treatment cycle visit, EoT visit, or day 30 safety follow-up visit. If regorafenib is discontinued first and the day 30 safety follow-up visit falls into pembrolizumab treatment or pembrolizumab day 30 follow-up visit, no separate regorafenib safety follow-up visit is necessary.

All pregnancies and exposure during breastfeeding should be collected from the start of study intervention through 120 days following discontinuation of study intervention, or 30 days following discontinuation of study intervention if the participant initiates new anti-cancer therapy.

Participants who discontinue study intervention due to radiologically confirmed PD will complete the mandatory safety follow-up visits.

Participants who discontinue from the study for any reason other than PD (or death, withdrawal of consent, or lost to follow-up) will be followed for progression during the active follow-up period. During the active follow-up period, computed tomography (CT) / magnetic resonance imaging (MRI) evaluations will be performed at efficacy follow-up visits (see the SoA in Section 1.3.1). In addition, study intervention-related toxicity/AE, information about survival status, and subsequent anti-cancer therapy will be followed up until completion of the active follow-up.

Active follow-up will be terminated by radiological PD, or the start of a new anti-cancer treatment, or death, or withdrawal of consent for further participation, or lost to follow-up.

4.1.1.4 Long-term Follow-up

All surviving participants will enter the long-term follow-up period after discontinuing from the active follow-up period except for participants who explicitly withdraw consent or are lost to follow-up.

Participants will be followed for OS and subsequent anti-cancer therapy at 3-month intervals (\pm 14 days) until the end of the study, withdrawal of consent, lost to follow-up, or death, whichever comes first (telephone contact is sufficient). Participants may be contacted at additional times throughout the course of the study in order to collect survival data to ensure that long-term follow-up data is current.

4.2 Scientific Rationale for Study Design

[figure not shown]
Recent clinical data support immunotherapy with checkpoint inhibitors as treatment options in first line for patients with advanced HCC. Although these drugs are available, a high unmet clinical need remains for the patients with advanced HCC who have progressed in first line treatment options with immunotherapy agents.

Regorafenib has established activity as a single agent and has been shown to provide survival benefit in HCC patients progressing on sorafenib treatment (Bruix et al. 2017). Pembrolizumab has been granted accelerated FDA approval for the treatment of HCC patients who have been previously treated with sorafenib (Zhu et al. 2018).

This study follows a two-phase design, consisting of an initial pilot phase and an expansion phase (Figure 4–2).

An interim analysis is planned when the last participant enrolled in each of the cohorts is assessed for ORR (as defined by RECIST 1.1) during at least two post-baseline scans, or has been followed for approximately 14 weeks from the first dose, unless they have discontinued before due to progression or any other reason. Both cohorts will be analyzed separately and no pause of recruitment is expected between the study phases until the results of the interim analysis become available.

Figure 4-2: Study Design and Planned Analyses

Participants recruited in the pilot phase to one or both cohorts that achieve the response rate criterion for expansion will also be analyzed as part of the expansion phase.

The expansion phase will continue until the achievement of the study primary completion parameters outlined in Section 4.4.

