8.10 Medical Resource Utilization and Health Economics

Not applicable.

9. Statistical Considerations

This is a single arm, Phase 2 study with ORR per RECIST1.1 by central review as the primary endpoint.

In the pilot phase of the study, the participant population for the expansion phase is determined. Participants from the pilot phase who match the population of the expansion phase (atezolizumab plus bevacizumab vs. atezolizumab plus bevacizumab and other first line treatments) will be included in the analysis of the expansion phase.

Historical (background) response rate is assumed to be 20% (per RECIST 1.1, an ORR of 7% was observed in the regorafenib arm of the HCC trial RESORCE (Bruix et al. 2017), and an ORR of 18% was observed in the pembrolizumab arm of the HCC trial KEYNOTE-240 (Finn et al. 2020); as the sum of the ORR was about 25%, in order to show a synergistic effect this study is designed to rule out an ORR of 20%). Target response rate (i.e. true underlying response rate for which there is 95% power conditional on a positive pilot phase) will be 35%.

In addition to the number of responders, totality of data including tumor dynamics response (depth, durability) and overall safety data will be considered to make a determination to move forward to the expansion phase.

A one-sided exact binomial test with a type-I error of 2.5% will be conducted at the end of the expansion phase to test the hypothesis.

Page 93 of 141

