9.1 Statistical Hypotheses

There will be no statistical hypothesis testing done in the pilot phase of the study.

The primary hypotheses to be tested in the expansion phase of the study is

H₀: ORR_{Combination} \leq 20% vs. H₁: ORR_{Combination} \geq 20%

The primary hypothesis will be tested by an exact binomial test. The significance level will be a 1-sided alpha of 2.5%.

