9.2 Sample Size Determination

It is expected that approximately 170 participants will be screened to achieve the 119 evaluable participants for both study phases combined.

Pilot phase: A total of approximately 52 participants will be enrolled to receive regorafenib in combination with pembrolizumab divided in two cohorts: 26 of them after atezolizumab plus bevacizumab treatment combination (cohort 1); and 26 after any IO containing first line treatment (cohort 2), excluding atezolimab plus bevacizumab treatment combination.

Expansion phase: 2 scenarios should be considered depending on the pilot phase results.

- **Scenario 1**: if in the pilot phase at least 8 responders out of the 26 treated in cohort 1 are observed
- Scenario 2: if in the pilot phase at least 8 responders in each cohort are observed

In scenario 1, the study can continue to accrue 67 new additional participants after atezolizumab in combination with bevacizumab (i.e. a total of 93 participants after prior treatment with atezolizumab in combination with bevacizumab will be enrolled, representing the patient population of cohort 1). If 27 or more participants respond out of 93 evaluable participants (i.e. ORR 29%), the study will have ruled out an ORR \leq 20% (with 1-sided alpha of 0.025), using an exact binomial test.

In scenario 2, the study can continue to accrue 67 new additional participants after any immune checkpoint inhibitor as defined in the pilot phase (i.e. a total of 119 participants will be enrolled, representing the patient population of cohort 1 and cohort 2). If 34 or more participants respond out of 119 evaluable participants (i.e. ORR 29%), the study will have ruled out an ORR \leq 20% (with 1-sided alpha of 0.025), using an exact binomial test.

In case cohort 2 meets the response rate criterion and cohort 1 does not, the future direction for further evaluation in the expansion phase will be decided based on the totality of data and treatment landscape at the time.

If the true underlying response rate is 35%, given that at least 8 responders are observed in stage 1, the conditional power for the final analysis is at least 95%, under both scenarios above.

Page 94 of 141

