9.4.1.2 Primary Efficacy Endpoint

The primary endpoint of the study is ORR based on RECIST 1.1 assessed by central review. ORR is defined as the proportion of participants with best overall response of confirmed CR or PR. Participants for whom best overall tumor response is not CR or PR, as well as participants without any post-baseline tumor assessment will be considered non-responders.

In both study phases, the primary efficacy variable will be analyzed after all participants are available for efficacy. The analysis will be done on the Full Analysis Set. In the pilot phase, the analysis will be done by cohort. In the expansion phase, the analysis will be done on the participants who received the first line treatment determined in the pilot phase of the study.

Methods used will include frequency tables (with the ORR table also including all "Best overall response" categories) as well as 95% two-sided Clopper-Pearson confidence intervals and the results of an exact binomial test.

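### If the study expands, the pooled final ORR carries an upward selection bias from the 8/26 pilot gate; supplementary estimates should be reported beside it

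*Protocol*

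**What the plan says.** Section 9.2 of the protocol sets two routes to expansion. Scenario 1 applies "if in the pilot phase at least 8 responders out of the 26 treated in cohort 1 are observed"; scenario 2 applies "if in the pilot phase at least 8 responders in each cohort are observed". Either route adds 67 new participants, giving 93 or 119 in total. Section 4.2 then carries the pilot data forward: "Participants recruited in the pilot phase to one or both cohorts that achieve the response rate criterion for expansion will also be analyzed" in the expansion phase. The opening of Section 9 says the same.

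Success is 27 or more responders of 93 in scenario 1. For scenario 2 the rule is: "If 34 or more participants respond out of 119 evaluable participants". On the level, Section 9.1 states: "The significance level will be a 1-sided alpha of 2.5" per cent. Section 9.4.1.2 reports frequency tables "as well as 95% two-sided Clopper-Pearson confidence intervals and the results of an exact binomial test". Section 9.5 calls the interim look a futility analysis and makes no type I error adjustment.

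No supplied text adjusts the estimate or its interval for the gate, or reports the 67 new participants separately. SAP v3.0 marks sensitivity and supplementary analyses of the primary endpoint (5.3.3, 5.3.4) as not applicable. For the main analysis it refers to SAP v2.0, which is not among the documents.

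**The concern.** A cohort reaches the final analysis only after an observed pilot rate of at least 8/26 = 30.8%. Some cohorts pass by luck, and that luck stays in the pooled proportion because the same participants are counted again. They make up 26/93 = 28% of the final sample in scenario 1 and 52/119 = 44% in scenario 2.

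In a single-arm study with ORR as primary endpoint, the estimate and its interval are the main efficacy output and would inform planning of any later trial. The inflation is largest when the true rate is modest, which is when the decision is hardest. The protocol sets 20% as the rate to exclude, against single-agent rates that it adds up to about 25%.

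**Working it through.** **Inputs (protocol Sections 9, 9.1, 9.2).** Null ORR 20%; target 35%; one-sided alpha 2.5%; gate at least 8/26 in cohort 1 (scenario 1) or in each cohort (scenario 2); 67 new participants; critical values 27/93 and 34/119.

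**1. The plan's own figures.** Exact binomial tails at 20%:
- P(X ≥ 27 | 93) = 0.0238, while P(X ≥ 26) = 0.0408.
- P(X ≥ 34 | 119) = 0.0158, while P(X ≥ 33) = 0.0264.
- Conditional power at 35%, given the gate: 95.5% (scenario 1) and 99.0% (scenario 2).

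Both critical values and the claim of at least 95% conditional power reproduce.

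**2. Model.** Let X ~ Bin(26, p) truncated to X ≥ 8, with one such cohort in scenario 1 and two independent ones in scenario 2. Let Y ~ Bin(67, p) be the new participants. Expected pooled ORR given the gate is (E[X | X ≥ 8] + 67p)/93, or (2·E[X | X ≥ 8] + 67p)/119.

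Example at p = 20%: P(X ≥ 8) = 0.131 and E[X | X ≥ 8] = 8.71, against 26 × 0.20 = 5.2 without selection. Scenario 1: (8.71 + 13.40)/93 = 23.8%. Scenario 2: (17.42 + 13.40)/119 = 25.9%.

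**3. Bias and coverage given the gate.** Coverage is the conditional probability that the ordinary Clopper-Pearson interval on 93 or 119 contains p.

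| True ORR | S1: P(gate) | S1: bias | S1: coverage | S2: P(gate) | S2: bias | S2: coverage |
|---|---|---|---|---|---|---|
| 20% | 13.1% | +3.8 | 89.8% | 1.7% | +5.9 | 77.9% |
| 25% | 31.5% | +2.8 | 95.8% | 9.9% | +4.3 | 87.8% |
| 30% | 54.0% | +1.9 | 96.9% | 29.1% | +2.9 | 95.1% |
| 35% | 74.0% | +1.1 | 97.1% | 54.8% | +1.8 | 96.3% |

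Scenario 2 misses are almost all on one side: the lower limit lies above the truth 22.1% of the time at 20% and 12.2% at 25%, against a nominal 2.5%. With unequal cohorts (20% and 35%, new participants split evenly), scenario 2 bias is +3.8 points and coverage 89.0%.

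**4. Type I error with the gate at 20%.** P(gate) × P(reject | gate): scenario 1, 0.1313 × 0.1025 = 1.35%; scenario 2, 0.0172 × 0.2209 = 0.38%. Both are below 2.5%.

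**5. At the success boundary.** The conditionally unbiased estimate averages (new responders)/67 over all splits of the total that satisfy the gate, weighted by the number of ways each split can arise.
- 27/93: raw 29.0% (Clopper-Pearson 20.1–39.4%); conditionally unbiased 26.7%; exact interval conditional on the gate 17.0–37.8%.
- 34/119: raw 28.6% (20.7–37.6%); conditionally unbiased 24.1%; conditional interval 15.1–34.4%.

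A check by hand agrees in direction. The gate guarantees at least 16 pilot responders in scenario 2, so at 34/119 the new participants contribute at most 18/67 = 26.9%. In scenario 1, at 27/93, they contribute at most 19/67 = 28.4%.

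**6. Behaviour of the alternatives.** Clopper-Pearson on the 67 new participants covers 96.1–96.9% at true rates of 20–35%. The exact conditional interval covers 95.6–96.7%. The conditional interval first excludes 20% at 30/93 and 39/119, so it still contains 20% at 27–29/93 and 34–38/119, where the planned test rejects.

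**The case against.** **The bias exists only given expansion.** Averaged over stopped and expanded trials in scenario 1, the bias is slightly negative (−1.3 to −2.6 points at 20–35%) and coverage is 95.4–98.1%. This stands, and whether to condition is a recognised choice. But the 93- or 119-participant figure exists only after expansion, so the conditional view is relevant to whoever reads that figure.

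**The poor coverage arises in rarely reached trials.** This stands; the gate probabilities belong beside the coverage figures. At the 35% target the bias is 1.1 to 1.8 points and coverage exceeds 95%.

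**An adjusted headline would clash with the test and is often less accurate.** This also stands. The planned Clopper-Pearson interval agrees with the planned test; the conditional interval does not at 27–29/93 and 34–38/119. Root mean squared error given the gate, pooled versus conditionally unbiased, is 4.76 versus 5.29 points in scenario 1 and 4.31 versus 4.88 in scenario 2 at 35%. The unbiased estimate is more accurate only at lower rates (20% in scenario 1, 20–25% in scenario 2). This argues for showing it beside the pooled result, not in its place.

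**The count rule is only part of the gate.** Section 9 also weighs the totality of data. Pilot counts may change between the look at about 14 weeks and the final confirmed best response. The figures above are therefore approximations.

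A reader might infer that re-using the pilot data inflates the type I error. It does not: the gate lowers it. Nor does 24.1% at 34/119 show that the combination fails to beat the single-agent sum of about 25%: the tested benchmark is 20%, and exactly 34/119 is one improbable result if the true rate is 35%.

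**Conclusion.** The point holds as a matter of estimation given expansion. Under the stated gate, the planned pooled ORR overstates the true rate by 1.1 to 3.8 points in scenario 1 and 1.8 to 5.9 points in scenario 2 across true rates of 35% down to 20%. The ordinary 95% interval falls clearly short only at low true rates: 20% in scenario 1, 20% and 25% in scenario 2. The hypothesis test needs no change.

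The figures assume that the go decision follows the count alone, that pilot counts do not change after the gate, and that both cohorts share one ORR.

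A reader might also conclude that the trial's reported ORR is inflated. The documents do not support that. The SAP version history records that recruitment stopped early, and the supplied SAP does not say whether expansion took place. Without expansion the point falls away. SAP v2.0, which holds the main analytical approach, was not available, so an adjustment there cannot be excluded.

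**What to change.** In protocol Section 9.4.1.2, and in SAP 5.3.4 in place of the not-applicable entry, keep the exact binomial test and the pooled ORR with its Clopper-Pearson interval as the primary report, labelled as unadjusted for the pilot selection. If expansion took place, add beside it:

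- (a) the ORR in the 67 newly enrolled participants with a Clopper-Pearson interval;
- (b) the conditionally unbiased two-stage estimate with an exact interval conditional on the gate, stating in advance that this interval can include 20% when the test rejects (27–29/93 or 34–38/119).

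If there was no expansion, one sentence in the SAP saying so closes the point.

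The cost is a little SAP text and programming, with no new participants or data. The supplementary intervals will be wider and the adjusted ORR somewhat less favourable than the pooled one.
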